#### **7.10.10.3 Tumor Dovitinib Pharmacokinetic Evaluation**

All patients will have a post-therapy dovitinib pharmacokinetic evaluation performed. Bladder biopsy tissue for the dovitinib pharmacokinetic evaluation should be collected on cycle 3 day 26 ( $\pm$  7 days) at the time of the first post-dovitinib TURBT. The biopsy tissue may be obtained from a bladder tumor region or from normal appearing urothelium.

Dovitinib tissue concentrations will be analyzed by mass spectroscopy and liquid chromatography methodologies developed specifically for this protocol by the IUSCC Clinical Pharmacology Analytical Core (CPAC). Refer to SPM for collection and shipping guidelines.

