### 3.3.1 Endpoint for Exploratory Objectives

- Presence of FGFR3 mutations (see Table 1-2) in tumor tissue and urine will be assessed by massively parallel sequencing of exons 7, 10, and 15 utilizing the Ion Torrent PGM instrument. Presence of FGFR3 mutations within patient free plasma will be assessed by PCR-amplification of the target regions and sequencing.
- Pre-treatment germline FGFR SNPs will be assessed by testing extracted DNA from patient PBMC's (collected prior to initiating dovitinib therapy) with validated commercial probes.
- Pre-treatment germline VEGFR SNPs will be assessed by testing extracted DNA from patient PBMC's (collected prior to initiating dovitinib therapy) with validated commercial probes.
- Presence of VEGFR over-expression within tumor tissue will be assessed and interpreted by standard immunohistochemistry analysis with appropriate controls.
- Pre- and post-treatment bladder tumor FGFR and VEGFR pathway phosphorylation changes will be assessed by bladder tumor tissue immunohistochemistry utilizing commercially available antibodies including, but not limited to, the following: FGFR3, pFGFR3, VEGFR2, pVEGFR2, FRS2, pFRS2, ERK, pERK.
- Post-treatment bladder tissue dovitinib concentrations will be assessed by TURBT fresh frozen tissue obtained at the 3-month cystoscopy
- Hypertension will be defined as a systolic blood pressure (SBP) of  $\geq 140$  mmHg or a diastolic blood pressure (DBP) of  $\geq 90$  mm Hg recorded at any time after dovitinib therapy is initiated.

Objectives and related endpoints are described in [Table 3-1](#) below.

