
complete response rate and 1-year relapse free survival rate in patients treated with dovitinib
 
 
• To characterize concordance rates between UC patient detected tumor, urine and circulating free plasma FGFR3 mutations
 
• To characterize post-treatment bladder tissue dovitinib concentrations
 
• To characterize VEGFR over-expression status within tumor tissue
 
	
diastolic blood pressure (DBP) of <math>\geq</math> 90 mm Hg recorded at any time after dovitinib therapy is initiated
 
Presence of FGFR3 mutation within patient tumor tissue, urine, will be assessed by massive parallel sequencing analysis of exons 7, 10, and 15 utilizing Ion Torrent PGM instrument. Presence of FGFR3 mutation within patient free plasma will be assessed by PCR-amplification of the target regions and sequencing
 
Post-treatment bladder tissue obtained at 3-month TURBT will be analyzed by IUSCC Clinical Pharmacology Analytical core according to standard commercial assays
 
Presence of VEGFR over-expression within tumor tissue will be assessed by standard IHC analysis
	

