**Figure 4-1 Study design**

#### 4.1.1 Investigational Treatment, Other Study Treatment, Study Treatment, Supportive Treatment

Investigational treatment in all patients will consist of oral dovitinib 500 mg taken once daily for 5 consecutive days followed by 2 days off repeated every week. Each treatment cycle will be defined as 28 days (4 weeks). In patients not experiencing significant toxicity or relapsed disease, a study-defined maximum number of dovitinib cycles will not be stipulated. Dovitinib will be supplied in the form of 100 mg hard gelatin capsules or film coated tablets.

Standard of care cystoscopy and urine cytology will be performed every 3 months  $\pm$  7 days during the first 12 months of follow-up and per the treating urologist's discretion thereafter. Standard of care tumor biopsy and bladder biopsies will be performed every 3 months  $\pm$  7 days during the first 6 months of follow-up and per the treating urologist's discretion thereafter.

Anti-emetic medications are permitted at the discretion of the treating physician.

Colony stimulating growth factor (i.e. erythropoietin, darbopoeitin, pegfilgrastim, etc.) support is permitted at the discretion of the treating physician.

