## 7 Visit schedule and assessments

### 7.1 Study Flow and Visit Schedule

[Table 7-1](#) lists all of the assessments except for laboratory assessments and indicates with an “X” the visits when they are performed. [Table 7-2](#) lists all laboratory assessments. All data obtained from these assessments must be supported in the patient’s source documentation. The table indicates which data are entered into the database (D) or may remain in source documents only (S) (column category). Assessments that generate data for the EDC system are listed.

Since dovitinib is given in a 5 days on/2 days off dosing schedule, day 12 assessments are intended to be performed on the last dosing day of the 2nd week in cycle 1 and cycle 2 and day 26 assessments are intended to be performed on the last dosing day of the 4th week in cycle 1 and cycle 2.

All assessments have a ±3 days window unless otherwise indicated. In the event of public holidays (e.g. Christmas, New Year’s Day), there is a ±5 days window on all assessments. Every effort must be made to follow the schedule of assessments within the windows outlined in the protocol. Additional assessment may be performed as clinically indicated.

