- g. Archived pre-treatment tissue samples for study correlates will be collected from enrolled eligible patients. Blood and urine samples for study correlates will be collected at Cycle 1 Day 1 from enrolled eligible patients. The correlative analyses will be completed in batch groupings at study completion. Refer to SPM for collection, processing and shipping guidelines.
- h. Tissue for dovitinib PK analysis will be collected at the initial post-treatment cystoscopy with TURBT performed 3 months +/- 7 days after starting dovitinib therapy. Refer to SPM for collection, processing and shipping guidelines.
- i. Unstained slides are to be submitted from the pre-treatment TURBT specimen and from the post-treatment cystoscopy with TURBT performed 3 months +/- 7 days after starting dovitinib therapy. Refer to SPM for collection and shipping guidelines.

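### The tissue PK biopsy is dated cycle 3 day 26 in one section and 3 months in others, and neither version controls or reports time since the last dose

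*Combined protocol and SAP*

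**What the plan says.** **Date of the biopsy.** Section 7.10.10.3 says the tissue "should be collected on cycle 3 day 26", with a ±7-day allowance, and ties it to the first TURBT after dovitinib. Table 7-1 footnote h takes the tissue from the initial post-treatment cystoscopy with TURBT "performed 3 months +/- 7 days after starting dovitinib therapy". The endpoint in section 3.3.1 uses "TURBT fresh frozen tissue obtained at the 3-month cystoscopy", and Table 3-1 has "Post-treatment bladder tissue obtained at 3-month TURBT". All of these mean one procedure.

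**Dosing calendar.** Section 4.1.1 sets 28-day cycles, with drug "taken once daily for 5 consecutive days followed by 2 days off repeated every week". Section 7.1 explains that "day 26 assessments are intended to be performed on the last dosing day" of week 4; it says this for cycles 1 and 2.

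**Analysis.** The pharmacokinetic set in section 10.2.4 takes every patient with evaluable post-treatment tissue data. Section 10.7.1 gives one pooled set of descriptive statistics and a boxplot. Neither mentions time since the last dose.

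**The concern.** There are two separate problems.

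First, one procedure has two nominal dates, each with its own ±7-day window. The protocol does not define 3 months in days. A site that is on schedule under one section may be recorded as deviating under the other.

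Second, no version of the date fixes how long after a dose the tissue is taken. Section 1.2.3 gives the purpose of the measurement: to confirm that the drug reaches the bladder, so that clinical outcomes can be interpreted. Section 1.2.2 says plasma concentration falls monoexponentially after its peak. If tissue follows at all, a low reading could mean poor penetration or simply a long interval since dosing. With about 20 patients and one sample each, a few late samples could move the pooled mean and median, and the planned summary would not show why.

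**Working it through.** **Inputs**
- Cycle length 28 days and weekly 5-on/2-off dosing: section 4.1.1.
- Cycle 3 day 26 ±7 days: section 7.10.10.3.
- 3 months ±7 days after starting drug: Table 7-1 footnote h.
- Assumptions: the first dose is study day 1, and dosing is uninterrupted.

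**Formulas**
- Study day = 28 × (cycle − 1) + cycle day.
- Position in week = ((study day − 1) mod 7) + 1. Positions 1 to 5 are dosing days; 6 and 7 are off days.

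**Reproducing the plan's own statement.** For cycle day 26, 25 mod 7 = 4, so the position is 5. This is the last dosing day of week 4, as section 7.1 says.

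**Date in 7.10.10.3.** 28 × 2 + 26 = 82. Since 81 mod 7 = 4, the position is 5, a dosing day. The window is days 75 to 89. Its off days are 76, 77, 83 and 84: 4 of 15, or 27%.

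**Date in footnote h, by reading of 3 months**

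| Reading | Study day | Position | Gap from day 82 | Window | Days shared with 75–89 | Off days in 15 |
|---|---|---|---|---|---|---|
| 12 weeks, as study day 84 | 84 | 7 (off) | 2 | 77–91 | 13 | 5 |
| 84 days after first dose | 85 | 1 (on) | 3 | 78–92 | 12 | 4 |
| Calendar months | 90 | 6 (off) | 8 | 83–97 | 7 | 5 |
| 13 weeks as study day 91, or calendar | 91 | 7 (off) | 9 | 84–98 | 6 | 5 |
| 91 days after first dose, or calendar | 92 | 1 (on) | 10 | 85–99 | 5 | 4 |
| Calendar months | 93 | 2 (on) | 11 | 86–100 | 4 | 4 |

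Taking every start date over four years, three calendar months falls on study day 90, 91, 92 or 93 in 6.0%, 14.8%, 21.4% and 57.8% of cases. It is an off day for about 21% of start dates.

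**Effect of the date conflict.** On the day-91 reading, biopsies on days 90 to 98 satisfy footnote h and fall outside 7.10.10.3. Those on days 75 to 83 do the reverse.

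**Effect of choosing one date.** The off-day share is 4/15 or 5/15 (27% or 33%) under every reading. A 15-day window over a 7-day pattern cannot avoid off days.

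**Time since last dose.** The last dose of a week is on position 5. At the usual dosing hour, the elapsed time is 24 h on position 6, 48 h on position 7 and 72 h on position 1 before that day's dose. The longest scheduled gap therefore falls on a calendar dosing day.

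**Possible size.** The documents give no plasma or tissue half-life. With an assumed half-life h of 6 to 36 h, the fraction left after t hours is 0.5^(t/h):
- 24 h: 6% to 63%
- 48 h: 0.4% to 40%
- 72 h: less than 0.1% to 25%

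The range is too wide to say whether the effect is trivial or dominant.

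**The case against.** The strongest reply is that every section names the same procedure, so sites would simply take the tissue at the first post-treatment TURBT. Three months can also be read as three 28-day cycles. Table 7-1 allows day 26 or 28 in later cycles, and cycle 3 day 28 is study day 84. The windows then share 12 or 13 of 15 days and the nominal gap is inside the ±7-day allowance. This stands as a plausible reading, but the protocol does not state it.

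Dosing is also a database item in Table 7-1, compliance is captured at each visit (section 6.2.4.1), and collection details are left to the study procedure manual, which is not available here. Last-dose time may already be collected. That could remove the data-capture request, but not the date conflict or the pooled summary in 10.7.1.

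A reader might draw three stronger inferences, which the documents do not support:
- **That the conflicting dates cause the mixing of on- and off-drug samples.** They do not. Either date alone gives 4 or 5 off days in 15, so reconciling them would leave the mixing in place.
- **That the 3-month date is an off-drug day.** This holds for study days 84, 90 and 91, but not for 85, 92 or 93. On calendar months it is a dosing day for about 79% of start dates.
- **That off-day samples are washed out.** Off days come 1 to 2 days after the last scheduled dose, no half-life is given, and section 1.2.2 describes extensive tissue distribution.

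**Conclusion.** The point holds in two limited parts. The biopsy date in 7.10.10.3 conflicts with section 3.3.1, Table 3-1 and Table 7-1 footnote h: the nominal gap is 8 to 11 days on a 13-week or calendar reading, and 2 to 3 days on a 12-week reading. Independently, time since last dose is neither controlled by any version nor used in the analysis, and 27% to 33% of the days in the window are off-drug whichever date is kept.

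The day counts assume uninterrupted dosing from study day 1. Actual gaps may be longer, since the footnotes to the section 6.1.4 table require discontinuation only for interruptions over 14 days. How much concentrations would differ cannot be stated without a half-life. The consequence is confined to one exploratory, descriptive endpoint; the primary endpoint, sample size and power are untouched. This is a minor, inexpensive improvement.

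**What to change.** 1. Reconcile section 7.10.10.3 with section 3.3.1, Table 3-1 and Table 7-1 footnote h, so that the biopsy has one nominal date and one window, stated in study days. Which date to keep is for the study team.
2. Record the date and time of the last dose and of the biopsy with each tissue sample, unless the study procedure manual already requires this.
3. In section 10.7.1, add a plot or listing of concentration against hours since last dose beside the pooled summary. A split by on-drug and off-drug calendar day is not enough, because it would class a pre-dose sample on the first dosing day of a week, with the longest scheduled gap, as on-drug.

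The cost is a wording correction, one data field and one extra summary. No change to dosing, visits or sample size is needed.

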Time-dependent PK of dovitinib was observed across all tested dose levels ranging from 50 to 600 mg/day. Following multiple daily administration at doses below 400 mg, the auto-induction of CYP1A1/A2 resulted in lower plasma exposure of dovitinib on day 7 (steady state) than that observed on day 1. However, after increasing the daily dose to 400 - 600 mg, TKI258 plasma concentration on day 7 was found to be similar to or greater than that on day 1, suggesting a more pronounced accumulation of dovitinib at higher doses. In addition, an over-proportional increase in dovitinib plasma exposure was observed with doses from 400 to 600 mg/day. The maximum tolerated dose of dovitinib for the continuous daily dosing schedule was 400 mg (study 2105).

The time-dependent PK and the nonlinear PK resulted in dose-dependent time to reach steady state, as well as dose-dependent accumulation at steady state. To prevent the prolonged and over-proportional accumulation in dovitinib exposure with dose escalation, an intermittent dosing schedule of 5 days on/2 days off was proposed for study 2107. At tested dose levels of 500 mg and 600 mg, no accumulation was observed on day 15 (steady state). The MTD for the 5 days on/2 days off dosing schedule was 500 mg (studies 2107 and 1101).

A human ADME (absorption, distribution, metabolism and excretion) study identified the major metabolites of dovitinib as C-hydroxyl metabolites (in feces) and an N-oxide (in plasma). These metabolites are more than 5-fold less pharmacologically active than the parent drug. The ADME study demonstrated that the majority of the dose administered was recovered from feces, and less than 21% of the dose was recovered in urine. In addition, the oral absorption of dovitinib was ~75% of the dose (2106).

Drug-drug interaction studies are ongoing. Available data from human, as well as *in vitro* studies, demonstrate that dovitinib has low or no inhibition potential for CYP450s. Therefore, dovitinib is not expected to cause inhibitory metabolic drug-drug interactions when co-administered with drugs metabolized by CYP450s. Dovitinib, however, does induce CYP1A2, CYP2C9 and CYP2C19; hence co-administration with substrates of CYP1A2/C9/C19 could reduce the exposure of these substrates.

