In addition, the ability to detect circulating tumor cells (CTCs) within the peripheral blood of cancer patients is well established (Yu et al., 2011). While promising, the current FDA approved CellSearch® technology has significant limitations including, but not limited to: 1) the need for real time analysis of specimens within 72 hours of collection; 2) the inability to do full genome profiling of CTC DNA/RNA; and 3) the dependence on tumor cells to express the pan-cytokeratin epithelial marker (EpCAM) on their cell surface and hence an inability to detect cells which have undergone epithelial to mesenchymal transformation (EMT). Accordingly, investigators have begun examining more readily available means to identify, quantify, and characterize tumor genomic content circulating within patients. The study of circulating free DNA/RNA (CFDNA/CFRNA) from peripheral blood and urine demonstrated feasibility in early studies (Gormally et al., 2007). A particular advantage of CFDNA/CFRNA platforms is the ability to analyze banked frozen patients samples. As a purely exploratory objective of this trial, we plan to assess the presence of FGFR3 mutations in patient baseline CFRNA from plasma and CFDNA from urine samples.

Lastly, while dovitinib has demonstrated excellent systemic bioavailability in oral form and the bladder epithelium is well vascularized, confirmation of dovitinib reaching its target will greatly enhance the clinical interpretation of patient outcomes at the completion of the study. As such, a final exploratory objective of this trial will be to measure bladder tissue concentrations of dovitinib at the initial post-treatment biopsy.

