**Table 6-2 Dose reduction steps for dovitinib**

Dose reduction*			
	Starting dose level - 0	Dose level - 1	Dose level - 2
Dovitinib	500 mg	400 mg	300 mg**
*Dose reduction should be based on the worst toxicity demonstrated at the last dose.			
**Dose reduction below 300 mg is not allowed.			

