ALT or AST > 3.0 x ULN AND Total Bilirubin > 2.0 x ULN	
Discontinue study treatment permanently.
 
Patients should be monitored weekly (including LFTse), or more frequently if clinically indicated, until ALT/AST and total bilirubin have resolved to ≤ grade 1 or stabilization (i.e., no CTCAE grade change over 4 weeks).

Renal	
Serum creatinine	
Grade 1 or 2	Maintain dose level
Grade 3	Delay study treatment until resolved to ≤ grade 1 or baseline, then ↓ 1 dose level
Grade 4	Discontinue study treatment
Amylase and/or lipase elevations	
Asymptomatic Grade 1 or 2	Maintain dose level
Asymptomatic Grade 3 or 4	Patients who develop grade 3 or 4 hyperlipasemia or hyperamylasemia without clinical or other evidence of pancreatitis may continue study medication without interruption
Pancreatitis	
Grade 2	Maintain dose level
Grade 3 or 4	Discontinue study treatment
Hand-foot syndrome	
Grade 1 or 2	Maintain dose level
Grade 3	Delay study treatment until resolved to ≤ grade 1 then ↓ 1 dose level
Grade 4	Discontinue study treatment
Other clinically significant adverse events	
Grade 1 or 2	Maintain dose level
Grade 3 (except hyperlipidemia d )	Delay study treatment until resolved to ≤ grade 1 or baseline, then maintain dose level or ↓ 1 dose level at the discretion of the investigator
Grade 4	Delay study treatment until resolved to ≤ grade 1 or baseline, then ↓ 1 dose level or discontinue dovitinib at the discretion of the investigator
All dose modifications should be based on the worst preceding toxicity.	
a Common Terminology Criteria for Adverse Events (CTCAE) v4.03	
b Patients are allowed two dose reductions: a dose reduction to 400 mg from 500 mg, and, if necessary, a dose reduction to 300 mg from 400 mg.	
c If a patient requires a dose interruption of > 14 days starting from the first day a dose was missed, then the patient must be discontinued from the study. Patients who discontinue the study for a study related adverse	

Toxicity intensity a	Dose modification b, c
event including an abnormal laboratory value must be followed at least once a week for 4 weeks and subsequently at 4 week intervals until resolution or stabilization of the event, whichever comes first.	

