#### **10.2.4 Pharmacokinetic Analysis Set**

The pharmacokinetic analysis set (PAS) consists of all patients who have evaluable pharmacokinetic (PK) data from post-treatment bladder tissue.

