#### **10.7.1 Exploratory Objectives Statistical Hypothesis, Model, and Method of Analysis**

All exploratory objectives are hypothesis generating in nature. Pre- and post-treatment phosphorylation changes in FGFR and VEGFR pathways will be analyzed by paired t-tests. FGFR SNPs, VEGFR SNPs, post-treatment hypertension, and baseline clinical factors of interest (e.g. age, ECOG PS, Charlson Comorbidity Index, gender, T1 vs. CIS, number of prior intravesical therapies, etc.) will be analyzed by univariate logistic regression and Cox regression for significant associations with 6-month CR and 1-year RFS rates, respectively. No multivariate models will be adopted given the small sample size. Concordance rates between tumor, urine, and circulating free plasma FGFR3 mutations will be summarized by Goodman-Kruskal gamma. The post-treatment bladder tissue dovitinib concentrations will be summarized by mean, standard deviation, minimum, median, maximum, and boxplot. Transformations to normality will be considered when necessary.

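### Month-3 dovitinib tissue levels from tumor and from normal urothelium go into one summary, so the planned summary does not identify the tumor concentration

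*Combined protocol and SAP*

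**What the plan says.** The purpose is given in section 1.2.3: "confirmation of dovitinib reaching its target will greatly enhance the clinical interpretation of patient outcomes". The objective itself (sections 3.3 and 10.7) is to characterize dovitinib concentrations in bladder tissue after treatment. Table 7-1 and the title of section 7.10.10.3 both label the measurement as tumor pharmacokinetics.

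On the sample, section 7.10.10.3 asks for biopsy tissue at the first TURBT on treatment, around month 3, and adds: "The biopsy tissue may be obtained from a bladder tumor region or from normal appearing urothelium". It gives no preference between the two, no pairing and no minimum number of tumor samples.

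On the analysis, the pharmacokinetic set in 10.2.4 "consists of all patients who have evaluable pharmacokinetic (PK) data from post-treatment bladder tissue". Section 10.7.1 states: "The post-treatment bladder tissue dovitinib concentrations will be summarized by mean, standard deviation, minimum, median, maximum, and boxplot". Neither section mentions tissue source.

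The visible text does not require the source of each sample to be recorded. Table 7-1 puts this assessment in the category that may stay in source documents, and collection details are left to the study procedure manual, which is not among the documents.

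**The concern.** The trial enrolls patients because their tumors carry an FGFR3 alteration (sections 2 and 5.1), so a reader will take confirmation that the drug reached its target to mean, at least in part, that it reached tumor. The planned mean, median and boxplot combine two kinds of tissue in unknown proportion and describe neither alone.

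The proportion is not random. A patient with residual tumor at month 3 can supply either tissue. A patient who is already tumor-free cannot supply tumor. The blend therefore shifts with early response.

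What is at stake is one exploratory result. If the source is not noted when the biopsy is taken, it may be hard to recover later, and the tumor question could then go unanswered.

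**Working it through.** The plan states no sample size, threshold or target concentration for this objective, so there is no figure of its own to reproduce. The check asks what the planned mean says about tumor.

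**Inputs.** From the documents: either tissue is allowed (7.10.10.3); there is one set and one summary (10.2.4, 10.7.1). Not in the documents, and so assumed over a range: the tumor share *f* of the samples, and the ratio *R* of the mean tumor level to the mean normal-urothelium level. The normal mean is set to 1.

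**Formula.** Pooled mean = *f* × *R* + (1 − *f*) × 1. Ratio of pooled mean to tumor mean = pooled mean / *R*.

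**Results.** Each cell gives the pooled mean, then its ratio to the tumor mean.

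| Tumor share *f* | *R* = 0 | *R* = 0.25 | *R* = 0.5 | *R* = 1 | *R* = 2 |
|---|---|---|---|---|---|
| 0 | 1.00; no finite ratio | 1.00; 4.0 | 1.00; 2.0 | 1.00; 1.0 | 1.00; 0.5 |
| 0.25 | 0.75; no finite ratio | 0.8125; 3.25 | 0.875; 1.75 | 1.00; 1.0 | 1.25; 0.625 |
| 0.50 | 0.50; no finite ratio | 0.625; 2.5 | 0.75; 1.5 | 1.00; 1.0 | 1.50; 0.75 |
| 0.75 | 0.25; no finite ratio | 0.4375; 1.75 | 0.625; 1.25 | 1.00; 1.0 | 1.75; 0.875 |

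Worked cell: *f* = 0.25 and *R* = 0.25 give 0.25 × 0.25 + 0.75 = 0.8125, and 0.8125 / 0.25 = 3.25.

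Three things follow.

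1. One pooled mean fits different tumor levels. A value of 0.75 arises with no drug in tumor (*f* = 0.25, *R* = 0) and with tumor at half the normal level (*f* = 0.50: 0.25 + 0.50 = 0.75).
2. With *f* = 0, which the text permits, the pooled mean is 1.00 whatever the tumor level.
3. If the two tissues have equal means (*R* = 1), pooling does not bias the mean. The documents give no data either way.

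The minimum and the boxplot do not solve this. A non-zero minimum shows that drug is present in tumor only if some samples are known to be tumor.

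**Side check on dose.** Patients may be at 500, 400 or 300 mg when sampled (Table 6-2). Assume a 60/25/15% mix and exposure proportional to dose: 0.60 × 1 + 0.25 × 0.8 + 0.15 × 0.6 = 0.89 of the 500 mg mean. Assume equal thirds and exposure proportional to dose squared: (1 + 0.64 + 0.36) / 3 = 0.67. Dose mixing lowers and spreads the summary, but by itself it does not hide whether drug is present.

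**The case against.** The strongest reply is that the objective can be met as worded. Every statement of it says bladder tissue, and 1.2.3 argues from oral bioavailability and the blood supply of the bladder lining. On that reading normal urothelium is a valid sample, and the flexibility lets every patient contribute. This stands for the formal objective. It does not remove the mismatch with the tumor labels in Table 7-1 and 7.10.10.3, or give a tumor level.

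It is also fair that pooling is inferred from silence. Section 10.7.1 does not forbid strata, 10.1 allows further exploratory analysis, and the procedure manual may already capture the source. If it does, individual tumor values could answer the question, so it would be too strong to say that the data cannot show whether drug reached tumor. The limit lies in the summary as planned.

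A reader might infer two larger problems.

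- **Dose.** Section 1.2.2 reports "an over-proportional increase in dovitinib plasma exposure was observed with doses from 400 to 600 mg/day", which suggests that mixing dose levels is a comparable defect. That sentence belongs to the account of daily dosing, its range does not reach 300 mg, and the next paragraph reports no accumulation at 500 and 600 mg on the 5-on/2-off schedule used here. Three dose levels are possible at sampling, not certain, and dose changes already go into the eCRF (6.1, 6.1.3).
- **Outcome.** A comparison of concentration with response would be confounded by tissue type. But 10.7.1 lists SNPs, hypertension and baseline factors for its regression models; tissue concentration is described only.

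**Conclusion.** The point holds as a minor one about interpretation. The planned summary can describe bladder-tissue exposure overall but does not identify the tumor concentration, and the mix of tissues depends on early response. The error could be nil if the two tissues have similar levels. Over the assumed range with 25% to 75% tumor samples, the pooled mean runs from 3.25 times the tumor mean (*R* = 0.25) down to 0.625 of it (*R* = 2), and it stays above zero even if tumor holds no drug. These sizes rest on assumed values of *f* and *R*; the documents support the ambiguity, not a particular magnitude.

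The conclusion also assumes that 10.7.1 is carried out as written, with one summary. It does not extend to dose level or to any link between concentration and outcome, and it does not touch the primary endpoint.

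**What to change.** Record the tissue source of each pharmacokinetic sample as tumor or normal urothelium, checked against the pathology of the same TURBT where available. The check matters because 7.10.7.1 calls for biopsies at all baseline tumor sites, and a former tumor site may hold no tumor by month 3.

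In 10.7.1, report concentrations separately by source with the number of samples in each, as individual values or a dot plot, each point marked with the dose level already held in the eCRF. State the tumor and normal-urothelium results separately. Base any statement about tumor on tumor samples only, and note that these come only from patients with residual tumor at month 3.

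The cost is one data item and a split display; no biopsy, visit or treatment rule changes. The downside is small groups. With 20 evaluable patients, a further split by three dose levels would average 20 / 6 = 3.3 per cell, which is why marking dose on the plot is preferable to separate tables.
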